5.1.1.3 Cohort B: Pembrolizumab plus mFOLFOX7 (Previously Untreated Participants)

mFOLFOX7 in combination with pembrolizumab will be explored. The starting dose for mFOLFOX7 is the standard dose routinely used in clinical practice and is described in Section 5.5.1.1.3. There will be no dose escalation of the standard dose of mFOLFOX7. If the standard dose mFOLFOX7 is deemed too toxic per mTPI, the dose of mFOLFOX7 may be de-escalated per [Figure 2](#), as outlined in Section 5.1.1. The dose of pembrolizumab will remain constant at 200 mg Q3W.

Abbreviations: BID = twice daily; DL = dose level; 5-FU = fluorouracil; mTPI = modified toxicity probability interval; RP2D = recommended Phase 2 dose; Q2W = every 2 weeks; Q3W = every 3 weeks.

[figure not shown]
Notes: DL1: standard dose. Please see Section 5.1.2 – Tolerability Evaluation Rules and Dose Finding.

DL-1: de-escalation dose

Figure 2 Study Diagram (Cohort B)

5.1.1.4 Cohort C: Pembrolizumab plus mFOLFOX7 plus Binimetinib (Previously Untreated Participants)

Participant may initiate enrollment in Cohort C after the preliminary RP2D decision has been made in Cohort B (pembrolizumab plus mFOLFOX7). Two dose levels of binimetinib (in combination with pembrolizumab and mFOLFOX7) will be explored. The starting dose of binimetinib will be 30 mg BID. The dose level of binimetinib will be escalated to 45 mg BID, based upon the occurrence of DLTs and the mTPI design rules as outlined in Section 5.1.1.

[figure not shown]
Abbreviations: BID = twice daily; DL = dose level; 5-FU = fluorouracil; mTPI = modified toxicity probability interval; RP2D = recommended Phase 2 dose; Q2W=every 2 weeks; Q3W=every 3 weeks.

Notes: DL1: standard dose. Please see Section 5.1.2 – Tolerability Evaluation Rules and Dose Finding.
DL2: escalation dose

Figure 3 Study Diagram (Cohort C)

5.1.1.5 Cohort D: Pembrolizumab plus FOLFIRI (Participants Previously Treated With One Line of Fluoropyrimidine plus Oxaliplatin-Based Therapy)

FOLFIRI in combination with pembrolizumab will be explored. The starting dose of pembrolizumab will remain constant at 200 mg Q3W. The starting standard dose for FOLFIRI is the dose routinely used in clinical practice and is described in Section 5.5.1.1.4. There will be no dose escalation of the standard dose of FOLFIRI. The dose level of FOLFIRI may be de-escalated per [Figure 4](#) based upon occurrence of DLTs and the mTPI design rules as outlined in Section 5.1.1.

[figure not shown]
Abbreviations: BID = twice daily; DL = dose level; 5-FU = fluorouracil; mTPI = modified toxicity probability interval; RP2D = recommended Phase 2 dose; Q2W = every 2 weeks; Q3W = every 3 weeks.

Notes: DL1: standard dose. DL-1: de-escalation dose.

Figure 4 Study Diagram (Cohort D)

5.1.1.6 Cohort E: Pembrolizumab plus FOLFIRI plus Binimetinib (Participants Previously Treated With One Line of Fluoropyrimidine plus Oxiplatin-Based Therapy)

Participant may initiate enrollment in Cohort E after the preliminary RP2D decision has been made in Cohort D (pembrolizumab plus FOLFIRI). Two dose levels of binimetinib (in combination with pembrolizumab and FOLFIRI) will be explored. The starting dose of binimetinib will be 30 mg BID. The dose level of binimetinib will be escalated to 45 mg BID, based upon the occurrence of DLTs and the mTPI design rules as outlined in Section 5.1.1.

Abbreviations: BID = twice daily; DL = dose level; 5-FU = fluorouracil; mTPI = modified toxicity probability interval; RP2D = recommended Phase 2 dose; Q2W = every 2 weeks; Q3W = every 3 weeks.

Notes: DL1: standard dose. Please see Section 5.1.2 – Tolerability Evaluation Rules and Dose Finding.

DL2: escalation dose

Figure 5 Study Diagram (Cohort E)

5.1.1.7 Part 2 (Dose Confirmation)

Each cohort can proceed to Part 2 independently after a preliminary RP2D for that cohort is identified in Part 1. In Part 2, approximately 16 additional participants per cohort will be treated at the doses identified using the mTPI design in Part 1 to ensure at least 30 participants are treated at RP2D.

5.1.1.8 Part 1 and Part 2

Participants in both parts of the trial may receive up to 2 years of treatment with pembrolizumab (35 administrations) and binimetinib and treatment will continue until disease progression, unacceptable AE(s), intercurrent illness that prevents further administration of treatment, investigator's decision to withdraw treatment, participant withdrawal of consent, pregnancy of the participant, noncompliance with trial treatment or procedure requirements, participant completes treatment, or administrative reasons requiring cessation of treatment. Treatment with SOC chemotherapy (mFOLFOX7 or FOLFIRI) will continue per Investigator's decision.

Participants will be monitored for the development of AEs, and for clinical and/or radiographic evidence of disease progression according to RECIST Version 1.1. However iRECIST could be used by the investigator for treatment decision. In participants who have initial evidence of radiological PD by RECIST Version 1.1, it will be at the discretion of the investigator whether or not to continue a participant on study treatment until repeat imaging is obtained to determine whether participant's disease is progressing or the initial evidence represents a 'pseudoprogression or tumor flare'. This clinical judgment decision should be based on the participant's overall clinical condition, including performance status, clinical symptoms, and laboratory data. Participants may continue to receive study treatment until tumor assessment is repeated ≥ 4 weeks later in order to confirm PD by iRECIST per site assessment.

Time period and frequency for collecting AE, SAE and other reportable safety event information is outlined in Section 9.3.1.

Participants who discontinue treatment for reasons other than confirmed disease progression will have post-treatment follow-up for disease status until disease progression, initiating a new anticancer therapy, withdrawing consent for trial participation, or becoming lost to follow-up, whichever occurs first.

After confirmed disease progression, each participant will be contacted (eg, by telephone) every 12 weeks for survival until withdrawal of consent to participate in the trial, becoming lost to follow-up, death, or end of the trial, whichever occurs first.

The trial will be conducted in conformance with GCP. Adverse events will be evaluated according to criteria outlined in the NCI CTCAE, Version 4.0 or later.

Specific procedures to be performed during the trial, as well as their prescribed times and associated visit windows, are outlined in the Schedule of Activities - Section 2.0. Details of each procedure are provided in Section 9.0 – Study Assessments and Procedures.

5.1.2 Tolerability Evaluation Rules and Dose Finding

Two dose levels of binimatinib and the dose levels for SOC chemotherapies (mFOLFOX7 and FOLFIRI) are provided in [Table 3](#). Dose escalation will continue as outlined above (Section 5.1.1) according to mTPI dose finding rules.

Table 3 Dose Levels in Cohorts A, B, C, D, and E (Parts 1 [Dose Finding] and 2 [Dose Confirmation])

Cohort	Dose Level	Regimen	
		Part 1 (Dose Finding)	Part 2 (Dose Confirmation)
Cohort A			
Pembrolizumab + Binimetinib	DL1	
 Pembrolizumab 200 mg IV Q3W Binimetinib 30 mg (oral) BID 	
 Pembrolizumab 200 mg IV Q3W + binimetinib (preliminary RP2D) (oral) BID
	DL2	
 Pembrolizumab 200 mg IV Q3W Binimetinib 45 mg (oral) BID 	
Cohort B			
Pembrolizumab + mFOLFOX7	DL1	
 Pembrolizumab 200 mg IV Q3W mFOLFOX7 (oxaliplatin [85 mg/m²]; leucovorin [calcium folinate] [400 mg/m²]; 5-FU [2400 mg/m² over 46-48 hrs]) IV Q2W 	
 Pembrolizumab 200 mg IV Q3W + mFOLFOX7 (preliminary RP2D) IV Q2W
	DL-1	
 Pembrolizumab 200 mg IV Q3W mFOLFOX7 (oxaliplatin [70 mg/m²]; leucovorin [calcium folinate] [400 mg/m²]; 5-FU [2000 mg/m² over 46-48 hrs]) IV Q2W 	
Cohort C			
Pembrolizumab + mFOLFOX7 + Binimetinib	DL1	
 Pembrolizumab 200 mg IV Q3W mFOLFOX7 (preliminary RP2D determined in Cohort B) IV Q2W Binimetinib 30 mg (oral) BID 	
 Pembrolizumab 200 mg IV Q3W + mFOLFOX7 (preliminary RP2D determined in Cohort B) IV Q2W + binimetinib (preliminary RP2D) (oral) BID
	DL2	
 Pembrolizumab 200 mg IV Q3W mFOLFOX7 [preliminary RP2D determined in Cohort B] IV Q2W Binimetinib 45 mg (oral) BID 	
Cohort D			
Pembrolizumab + FOLFIRI	DL1	
 Pembrolizumab 200 mg IV Q3W FOLFIRI (irinotecan [180 mg/m²]; leucovorin [calcium folinate] [400 mg/m²]; 5-FU [2400 mg/m² over 46-48 hrs]) IV Q2W 	
 Pembrolizumab 200 mg IV Q3W + FOLFIRI (preliminary RP2D) IV Q2W
	DL-1	
 Pembrolizumab 200 mg IV Q3W FOLFIRI (irinotecan [150 mg/m²]; leucovorin (calcium folinate) [400 mg/m²]; 5-FU [2000 mg/m² over 46-48 hrs]) IV Q2W 	
Cohort E			
Pembrolizumab + FOLFIRI + Binimetinib	DL1	
 Pembrolizumab 200 mg IV Q3W FOLFIRI [preliminary RP2D determined in Cohort D] IV Q2W Binimetinib 30 mg BID 	
 Pembrolizumab 200 mg IV Q3W + FOLFIRI (preliminary RP2D determined in Cohort D) IV Q2W + binimetinib (preliminary RP2D) BID
	DL2	
 Pembrolizumab 200 mg IV Q3W FOLFIRI [preliminary RP2D determined in Cohort D] IV Q2W Binimetinib 45 mg (oral) BID 	

Abbreviations: BID=twice daily; DL=dose level; DL1=standard dose; DL-1=de-escalation dose; DL2=escalation dose; 5-FU = fluorouracil; hrs = hours; Q2W = every 2 weeks; Q3W = every 3 weeks.

Individual participant dose interruptions and modifications may be implemented based on toxicity as described in Section 7.2.1. However, dose adjustments should not be made during the DLT observation period without discussion with the Sponsor.

The decision to enroll participants in the next dose level will be made by the sponsor in consultation with the participating investigators after reviewing the safety data.

Participants may continue on treatment until disease progression, unacceptable toxicity, investigator's decision to withdraw the participant, withdrawal of consent, development of an inter-current condition precluding further administration of study treatment, pregnancy of the participant, failure to comply with dosing evaluations or other study requirements, or administrative reasons.

5.1.3 Definition of Dose Limiting Toxicity

All toxicities will be graded using NCI CTCAE Version 4.0 based on the investigator assessment. The DLT window of observation will be during first **21-days** of treatment for Cohort A and first **28-days** of treatment for Cohorts B, C, D, and E to align with chemotherapy regimen.

The occurrence of any of the following toxicities will be considered a DLT, if assessed by the investigator to be possibly, probably or definitely related to study drug administration, excluding toxicities clearly not related to the drug, such as disease progression, environmental factors, unrelated trauma, etc.:

1. Grade 4 non-hematologic toxicity (not laboratory).
2. Grade 4 hematologic toxicity lasting >7 days.
3. Grade 3 thrombocytopenia associated with clinically significant bleeding.
4. Any non-hematologic AE Grade ≥ 3 in severity despite optimal supportive care should be considered a DLT, with the following exceptions:
 - Grade 3 fatigue lasting ≤ 3 days;
 - Grade 3 diarrhea, nausea, or vomiting without use of anti-emetics or anti-diarrheals per SOC;
 - Grade 3 rash without use of corticosteroids or anti-inflammatory agents per SOC.
5. Any Grade 3 or Grade 4 non-hematologic laboratory value if:
 - Medical intervention is required to treat the participant, or
 - The abnormality leads to hospitalization, or
 - The abnormality persists for >1 week.
6. Febrile neutropenia Grade 3 or Grade 4:
 - Grade 3 is defined as ANC $<1000/\text{mm}^3$ with a single temperature of $>38.3^\circ\text{C}$ (101°F) or a sustained temperature of $\geq 38^\circ\text{C}$ (100.4°F) for more than 1 hour.

- Grade 4 is defined as ANC <1000/mm³ with a single temperature of >38.3 degrees C (101 degrees F) or a sustained temperature of ≥38 degrees C (100.4 degrees F) for more than 1 hour, with life-threatening consequences and urgent intervention indicated.

7. Any prolonged delay (>2 weeks) in initiating study therapy due to a treatment-related AE that started during the DLT period:

8. Any treatment-related toxicity that causes the participant to discontinue treatment during the DLT period.

9. Missing >25% of binimetinib doses as a result of drug-related AE(s) during the DLT period.

10. Grade 5 toxicity

11. Cardiac disorders

- Absolute decrease in LVEF >10% compared with baseline and the LVEF is below the institution's lower limit of normal
- Left ventricular systolic dysfunction Grade ≥3
- Other cardiac disorders Grade ≥3

12. Vascular disorders

- Hypertension CTCAE Grade ≥3 requiring more than 1 drug or more intensive therapy
- Grade 4 hypertension

13. Eye disorders

 Retinal

- Retinopathy or retinal detachment Grade ≥3, confirmed by ophthalmic examination
- Retinal vein disorder including RVO, confirmed by ophthalmic examination

 Visual disturbances without ocular (retinal) changes

- Blurred vision, flashing lights, floaters: Grade ≥3

 Other specify

- Grade ≥3 for >21 consecutive days
- Grade 4 confirmed by ophthalmic examination

If a participant experiences a DLT, trial treatment may be discontinued following discussion between the sponsor and Investigator. However, if the participant is deriving clinical benefit as determined by the Investigator from the trial treatment, the participant may be allowed to continue after discussion between the sponsor and the Investigator.

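### DLT item 3 counts Grade 3 thrombocytopenia with a clinically significant bleed but not Grade 4 of 7 days or less with the same bleed, a gap mainly in Cohorts B and D

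*Combined protocol and SAP*

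**What the plan says.** DLT incidence is the primary endpoint (section 4) and drives the mTPI dose decisions (section 5.1.1.1). Section 5.1.3 applies to events the investigator considers possibly, probably or definitely related to study drug. Any single item is enough: "The occurrence of any of the following toxicities will be considered a DLT". The items that matter here are:

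- Item 1: "Grade 4 non-hematologic toxicity (not laboratory", so laboratory values are carved out.
- Item 2: "Grade 4 hematologic toxicity lasting >7 days".
- Item 3: "Grade 3 thrombocytopenia associated with clinically significant bleeding".
- Item 4: any non-hematologic AE of Grade 3 or above "in severity despite optimal supportive care should be considered a DLT, with the following exceptions". The exceptions cover fatigue, gastrointestinal symptoms and rash, not laboratory values.
- Item 5: "Any Grade 3 or Grade 4 non-hematologic laboratory value if" one of three conditions holds: intervention, hospitalization, or persistence beyond 1 week.
- Item 7: a delay of more than 2 weeks "in initiating study therapy due to a treatment-related AE that started during the DLT period".
- Item 8: "Any treatment-related toxicity that causes the participant to discontinue treatment during the DLT period".
- Item 9: more than 25% of binimetinib doses missed because of drug-related AEs.

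Section 5.1.4 replaces a participant who received less than 90% of the chemotherapy in the DLT period without having a DLT, and does not count that participant in the cohort total.

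**The concern.** Item 3 names Grade 3 alone. Items 4, 11, 12 and 13 write Grade ≥3 where that is meant, so the literal reading of item 3 excludes Grade 4. Item 2 then adds a duration threshold for Grade 4. Together they rank the same bleed in the wrong order: it is a DLT at the lower platelet grade, and may not be one at the higher grade if the episode is short. No clinical reason is given.

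What is at stake is whether a toxicity the protocol evidently regards as dose limiting enters the count that sets the dose. The replacement rule can add to this, because a participant whose event is not a DLT and who missed chemotherapy is removed rather than counted.

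A smaller point runs the other way. Item 4 lacks item 1's laboratory exclusion, so a short laboratory abnormality that item 5 was written to leave out could be read as a DLT.

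**Working it through.** **1. Which items can catch the event.** Take Grade 4 thrombocytopenia of 7 days or less with a clinically significant bleed below Grade 3, occurring while platelets are at Grade 4.

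| Item | Met? |
|---|---|
| 2 | No: needs more than 7 days |
| 3 | No: names Grade 3 only |
| 1, 4, 10 | No: the bleed is below Grade 3 (a Grade 3 or higher bleed could meet item 4) |
| 7 | Only if the delay exceeds 2 weeks |
| 8 | Only if the toxicity leads to discontinuation in the window |
| 9 | Not applicable in B and D (no binimetinib); in C and E needs more than 14 of 56 doses missed (28 days × 2 = 56; 25% = 14) |

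**2. Where item 8 closes the gap.** Appendix 5 makes attribution to the whole combination the general rule. Binimetinib is then implicated in A, C and E. Table 7 requires permanent discontinuation for other related Grade 4 AEs, and item 8 follows (reading a stop of one component as discontinuing treatment). Table 6 does the same for a Grade 4 immune-related event attributed to pembrolizumab.

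In B and D there is no binimetinib rule, and Table 6 applies only if the event is judged immune-related. Sections 7.2.1.4 and 7.2.1.5 leave delay and restart to the site and recommend 20% reductions, so item 8 need not be met. The same holds in C or E if the event is attributed to chemotherapy alone, which section 7.2.1.1 permits.

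**3. The replacement rule.** Chemotherapy is given every 14 days, so Days 1 and 15 fall in the 28-day window.

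- Day 15 dose skipped, or moved to Day 29: in the move, the delay is 29 − 15 = 14 days, exactly 2 weeks, so item 7 is not met. Chemotherapy received is 1/2 = 50%, below 90%. The participant is replaced.
- Day 15 dose reduced by 20%: (1 + 0.8)/2 = 90%, not below 90%. The participant stays in as a non-DLT.

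Section 10.5.1, read alone, would keep a participant observed for 28 days in the DLT analysis, but still as a non-DLT. The event is counted under neither section. The pembrolizumab and binimetinib rules in 5.1.4 keep anyone with a drug-related event; only the chemotherapy rule requires a DLT.

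**4. What one event can do.** Table 2 is redacted, so mTPI settings are assumed: Beta(1,1) prior, target 0.30, half-width 0.03 or 0.05, exclusion cutoff 0.95. These reproduce the protocol's example: P(rate > 0.30 | 4/6) = 0.971, above the cutoff, against 0.874 for 3/6. Under them, 1/3 is stay and 2/3 is de-escalate.

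With the Beta(1,1) prior of section 10.6.2 and the cap of 14 in section 10.9, one more DLT moves the posterior mean by 1/16 = 6.25 points. For example:

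- 3/14: mean 4/16 = 25.0%, 80% interval 12.2% to 39.3%
- 4/14: mean 5/16 = 31.3%, 80% interval 17.2% to 46.4%

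Both 3/14 and 4/14 are stay decisions under the assumed settings. These figures hold for any single DLT and do not measure this fault.

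**5. Items 4 and 5.** Appendix 5 makes a laboratory abnormality an AE when the investigator judges it clinically significant. A Grade 3 laboratory AE lasting 1 week or less, without intervention or hospitalization, fails item 5, yet no exception in item 4 removes it.

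**The case against.** The strongest reply is that the residual case is narrow. It needs a short Grade 4 episode, a bleed that is clinically significant but below Grade 3 and confined to the Grade 4 phase, Cohort B or D (or chemotherapy-only attribution in C or E), and no item 7, 8 or 9. An episode that reaches Grade 4 usually passes through Grade 3, each grade change is recorded (Appendix 5), and item 3 requires association with bleeding, not simultaneity. Section 5.1.2 calls for discussion with the sponsor before dose adjustments in the DLT window. Section 5.1.1.1 has the totality of the data reviewed before Part 2.

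Most of this stands as a limit on reach. It does not repair the rule: item 3 does not say that a Grade 4 episode qualifies through its Grade 3 phase, and sponsor discussion makes a missed dose harder to overlook without making the event a DLT.

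On items 4 and 5, one can argue that item 5 is the specific laboratory rule, and that an abnormality needing no treatment cannot persist despite optimal supportive care. That is a fair reading. The point is an ambiguity, and any error would over-count DLTs.

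A reader might also infer a missed DLT from item 13, whose duration of more than 21 days for other Grade ≥3 eye events cannot be completed in Cohort A's 21-day window. The documents do not support that: item 4 already covers such events, with items 8 and 9 behind it.

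**Conclusion.** The inconsistency in item 3 is real on the text and affects the primary endpoint's definition. Its practical reach is limited, mainly to Cohorts B and D. This rests on the literal reading of Grade 3, on combination attribution being the default, and on item 8 being met when binimetinib or pembrolizumab is permanently stopped in the window.

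A reader might infer that dose decisions were biased, or that the events are known to occur because section 3.2.1.2.2 reports one Grade ≥3 thrombocytopenia with binimetinib plus mFOLFOX7. The documents do not support either inference. That report does not say the event was Grade 4 or involved bleeding, and it describes the combination as free of DLTs. No event rate or size of effect on dose finding can be derived. The overlap of items 4 and 5 is a secondary clarification.

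**What to change.** In item 3, replace Grade 3 with Grade ≥3 and leave the rest of the item unchanged. Then re-check the DLTs already classified, and the participants replaced under the below-90% chemotherapy rule, against the new wording.

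In item 4, add a parenthesis: not laboratory; see item 5.

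The cost is two wording changes and one pass through the DLT and replacement listings. No additional data are needed.

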5.1.4 Replacement of Participants in DLT Period

[figure not shown]
To fully evaluate the safety of the combination therapy in this study, all participants enrolled must meet the criteria for evaluability during the DLT period. Participants are considered non-evaluable and will be replaced if:

- They are enrolled but not treated,
- They discontinue from the trial prior to completing all safety evaluations due to reasons other than drug-related AEs,
- They received <90% of the total pembrolizumab infusion during the DLT period (eg, because the infusion had to be discontinued due to an infusion reaction) and did not experience a drug-related event,
- They received <90% of the total SOC (mFOLFOX7 and FOLFIRI) infusion during the DLT period (eg, if the infusion had to be discontinued due to an infusion reaction) and did not experience a DLT,
- They received $\leq 75\%$ of binimetinib doses intended for the trial during the DLT period and did not experience a drug-related event,
- They must take a prohibited concomitant medication during the DLT period, unless this medication is used to treat a study drug-related AE,
- They must undergo medical/surgical procedures or have logistical issues not related to study therapy (eg, elective surgery, unrelated medical events) during the DLT period.

Non-evaluable participants will not be counted toward the cohort total for DLT evaluation.

Specific procedures to be performed during the trial, as well as their prescribed times and associated visit windows, are outlined in the Trial SoA - Section 2. Details of each procedure are provided in Section 9 – Study Assessments and Procedures.

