5.1.1 Study Design

5.1.1.1 Part 1 (Dose Finding)

An mTPI design [Ji Y, Li Y, Bekele BN 2007] with a target DLT rate of approximately 30% will be applied to identify a preliminary RP2D in each cohort.

Dose escalation and de-escalation decisions are based on the mTPI design as outlined in [Table 1](#).

For **Cohort A**, the DLT observation period is the first **21-days** of Cycle 1 and the next dose level may open for enrollment once the 21-days DLT observation period of the previous dose is completed and a dose escalation decision is made.

For **Cohorts B, C, D, and E**, the DLT observation period is the first **28-days** to accommodate the chemotherapy schedule and the next dose level may open for enrollment once the 28-days DLT observation period of the previous dose is completed and a dose decision (escalation or de-escalation) is made.

During dose finding, a minimum of 3 participants are required at each dose level, and up to 6 participants may be enrolled in the same cycle at each new dose. In [Table 2](#), the columns indicate the numbers of participants treated at the current dose level, and the rows indicate the numbers of participants experiencing DLT. The entries in the table are the dose-finding decisions: E, S, D, and DU represent escalating the dose, staying at the same dose, de-escalating the dose, and excluding the dose from the trial due to unacceptable toxicity, respectively.

Based on the mTPI design, the number of participants who are enrolled at a dose but are not yet fully evaluable for DLT assessment may not exceed the number of remaining participants who are at risk of developing a DLT before the dose would be considered unacceptably toxic

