([Table 2](#)). For example, if 1 out of 3 participants at a given dose level experiences a DLT, no more than an additional 3 participants may be enrolled at this dose level until additional DLT data are available since this dose would be considered unacceptably toxic if all 3 of the additional participants experience a DLT (ie, 4 out of 6 participants). New participants will be enrolled to the next dose level based on the decision as outlined in the mTPI design (see [Table 2](#)). There will be no intra-participant dose level escalation or dose level de-escalation for participants enrolled in this study (ie, 1 participant will be assigned to 1 dose level of the study drug). The definition of DLTs and the criteria for dose modification are outlined in Sections 5.1.3 and 7.2, respectively. The dose with an estimated DLT rate closest to 30% may be treated as a preliminary RP2D. Based on the emerging safety and/or efficacy signals, an alternate dose level may be explored.

The totality of the data will be considered before deciding on the dose(s) to carry forward to Part 2.

[figure not shown]
CCI

Treatment allocation will be accomplished by non-random assignment. If a participant meets the eligibility criteria for Cohorts B and C (i.e., previously untreated) or Cohorts D and E (i.e., previously treated with one line of fluoropyrimidine-based therapy) then IVRS/IWRS will alternate assignments between the 2 cohorts with the same eligibility criteria. Treatment for each cohort in Part 2 will begin once a preliminary RP2D for that cohort is identified in Part 1.

5.1.1.2 Cohort A: Pembrolizumab plus Binimetinib (Participants Previously Treated with Fluoropyrimidine, Irinotecan, and Oxaliplatin)

The dose of pembrolizumab will remain constant at 200 mg Q3W (see Section 5.5.1.1.1). Two dose levels of binimetinib will be explored: 30 mg BID and 45 mg BID. The starting dose of binimetinib will be 30 mg BID and is described in Section 5.5.1.1.2. The dose level of binimetinib will be escalated to 45 mg BID, based upon the mTPI design rules, as outlined in Section 5.1.1.

[figure not shown]

Abbreviations: DL = dose level; 5-FU = fluorouracil; mTPI = modified toxicity probability interval; RP2D = recommended Phase 2 dose; Q3W = every 3 weeks.

Figure 1 Study Diagram (Cohort A)

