10.6.2 Statistical Methods for Safety Analysis

Safety and tolerability will be assessed by clinical review of all relevant parameters including AEs, SAEs, ECIs, laboratory tests, vital signs, ECG measurements, and physical examinations.

[figure not shown]
Adverse events will be summarized by counts and frequencies for each dose level. Laboratory tests, vital signs, and other safety endpoints will be summarized as appropriate.

For Part 1 in each cohort: DLTs will be listed, and further summarized by dose level. The estimates of the DLT rates among participants treated at the RP2D and the 80% Bayesian credible intervals based on a prior distribution of Beta (1,1) for the estimates will be provided.

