10.9 Sample Size and Power Calculations

For each of the combinations, for Part 1 – dose finding phase: With sample size capped at 14 in each dose level, the maximum sample size in Part 1 is expected to be approximately 28 evaluable participants. In Part 2 – dose confirmation phase, approximately 16 additional participants per cohort will be treated at the RP2D identified in Part 1 to bring the total number of evaluable participants in Part 1 and Part 2 treated at RP2D to approximately 30 for each cohort. The actual sample size depends on the safety profiles and number of doses to be studied. A target sample size of 159 participants will be used for trial planning purposes. The key efficacy endpoint will be ORR based on the investigator assessment per RECIST 1.1. [Table 12](#) shows the ORR estimate and 95% CI (Clopper-Pearson interval) in each cohort.

Table 12 Estimate and 95% Confidence Interval of Objective Response Rate in Each Cohort

CCI

Abbreviations: CI=confidence interval; CR=complete response; ORR=objective response rate; PR=partial response.

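### Section 5.1.4 replaces and does not count some participants who already had a DLT, while Section 10.5.1 keeps them; the two rules need to name the same DLT-evaluable set

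*Combined protocol and SAP*

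**What the plan says.** Section 5.1.4 gives seven grounds for treating a participant as non-evaluable and replacing that participant. They fall into three groups.

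- **No DLT possible:** enrolled but never treated.
- **Observed toxicity protected:** the three under-dosing bullets. The chemotherapy bullet applies only to participants without a DLT. The pembrolizumab and binimetinib bullets apply only to those without a drug-related event.
- **No exception for a DLT already observed:** the remaining three bullets.
  - The bullet about early exit reads: "They discontinue from the trial prior to completing all safety evaluations due to reasons other than drug-related AEs"
  - The bullet about unrelated interventions or practical problems begins: "They must undergo medical/surgical procedures or have logistical issues not related to study therapy"
  - The bullet about excluded drugs reads: "They must take a prohibited concomitant medication during the DLT period, unless this medication is used to treat a study drug-related AE"

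The section then states the consequence: "Non-evaluable participants will not be counted toward the cohort total for DLT evaluation".

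Section 10.5.1 defines the set for DLT evaluation differently. It takes treated participants who were either observed for the full 21 days (Cohort A) or 28 days (Cohorts B to E), or who had a DLT before that window ended. It has no replacement exception.

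Dose finding uses an mTPI design "with a target DLT rate of approximately 30% will be applied to identify a preliminary RP2D" (Section 5.1.1.1).

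**The concern.** The leaving and medication bullets do contain exemptions, but these depend on why the participant left or why the drug was given, not on whether a DLT had already happened. The procedures and logistics bullet has no exemption at all.

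The situation can arise. Section 5.1.3 allows a participant with a DLT to continue treatment after discussion with the sponsor. That person is still inside the window and may later withdraw consent for an unrelated reason or need an unrelated procedure. Section 5.1.4, read literally, then requires replacement and leaves the event out of the count.

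DLT incidence is the primary endpoint and drives the dose decisions, with as few as 3 participants at a level. If the operational team follows Section 5.1.4 and the analysis follows Section 10.5.1, the preliminary RP2D rests on one count and the reported DLT rate on another.

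**Working it through.** **Inputs from the documents.** Target DLT rate 0.30 (Section 5.1.1.1). At least 3 participants per level (Section 5.1.1.1) and a cap of 14 (Section 10.9: "With sample size capped at 14 in each dose level"). One stated boundary, from the example that starts at 1 DLT in 3: "this dose would be considered unacceptably toxic if all 3 of the additional participants experience a DLT", that is, 4 of 6 (Section 5.1.1.1).

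**Assumptions.** Table 2 is not visible in the public document, so its other cells were rebuilt. Section 10.6.2 gives a prior for the DLT-rate estimates ("based on a prior distribution of Beta (1,1) for the estimates"), and I assume the same prior for the dose rules. I also assume an equivalence half-width of 0.05 (0.03 gives an identical table) and exclusion (DU) when Pr(p > 0.30) exceeds 0.95.

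**Step 1: reproduce the stated boundary.** With x DLTs in n participants the posterior is Beta(1+x, 1+n−x).

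- 4/6: Beta(5,3), Pr(p > 0.30) = 0.971 > 0.95, so DU. This matches the protocol.
- 3/6: Beta(4,4), Pr(p > 0.30) = 0.874, so not DU.

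**Step 2: decisions at small n.** If the dose is not excluded, the decision is the interval with the largest posterior probability per unit width:

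- E = F(0.25)/0.25
- S = [F(0.35) − F(0.25)]/0.10
- D = [1 − F(0.35)]/0.65

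| x/n | F(0.25) | F(0.35) | E | S | D | Decision |
|---|---|---|---|---|---|---|
| 0/3 | 0.684 | 0.821 | 2.73 | 1.38 | 0.27 | Escalate |
| 1/3 | 0.262 | 0.437 | 1.05 | 1.75 | 0.87 | Stay |
| 2/3 | 0.051 | 0.126 | 0.20 | 0.76 | 1.34 | De-escalate |
| 3/6 | 0.071 | 0.200 | 0.28 | 1.29 | 1.23 | Stay |

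**Step 3: remove one DLT and add a DLT-free replacement,** so x/n becomes (x−1)/n.

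- 1/3 stay becomes 0/3 escalate.
- 2/3 de-escalate becomes 1/3 stay.
- 4/6 unacceptable becomes 3/6 stay.

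For every n from 3 to 14 and every x ≥ 1 there are 3 + 4 + … + 14 = 102 cells. Of these, 31 move to a less restrictive decision, 71 do not change and none becomes more restrictive. If the replacement also has a DLT, the count returns to x/n and nothing changes.

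**Step 4: the two sections side by side.** Take 1 DLT in 3, where the DLT participant then meets one of the three bullets and the replacement has no DLT. Section 5.1.4 counts 0/3 (escalate). Section 10.5.1 keeps the original participant as well as the replacement, giving 1/4, which the rebuilt table reads as stay.

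**Step 5: can a bias in the DLT rate be stated?** Let f be the share of DLT participants, and g the share of DLT-free participants, removed by these bullets. The counted rate is p(1−f)/[p(1−f) + (1−p)(1−g)]. At p = 0.30:

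- f = 10%, g = 0: 0.27/(0.27 + 0.70) = 27.8%
- f = g = 10%: 0.27/(0.27 + 0.63) = 30.0%
- f = 0, g = 10%: 0.30/(0.30 + 0.63) = 32.3%

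The documents give neither f nor g, so neither the size nor the sign follows from them.

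**The case against.** The strongest answer is that Section 10.5.1 already keeps any participant with a DLT in the window, so the analysed primary endpoint does not lose the event. That stands, and it makes this a conflict between two sections rather than an unopposed rule that deletes DLTs. It does not remove the problem. Section 5.1.4 is the operational rule for who is replaced and counted while doses are being decided, and nothing says that Section 10.5.1 overrides it.

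The case is also narrow. Exits caused by drug-related AEs, and prohibited medication used to treat them, fall outside the bullets. Stopping treatment for progression would not by itself trigger the leaving bullet: Section 8.1 separates stopping treatment from leaving the study, and the first scheduled on-study scan is at week 9, after the window. The sponsor's safety review (Section 5.1.2) and the review of all data before Part 2 (Section 5.1.1.1) might catch an individual case, although neither is written as an exception to Section 5.1.4.

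A reader might infer two stronger things. One is that the rule always pushes towards escalation. The documents do not support that: 71 of 102 rebuilt cells do not move, a replacement with a DLT restores the count, and Cohorts B and D have no escalation step, so the most that can happen there is a missed de-escalation or exclusion. The other is that the DLT rate is biased downwards by a calculable amount. That requires DLT participants to be removed more often than DLT-free ones, and the documents give no figure for either.

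**Conclusion.** The point holds in a limited form. Three bullets of Section 5.1.4 lack the protection for observed toxicity that the under-dosing bullets have, and for a participant with a DLT who later meets one of them, Sections 5.1.4 and 10.5.1 give opposite answers. Losing one DLT this way, with a DLT-free replacement, never makes the mTPI decision more restrictive, and at 3 to 6 participants it can make it less so. Apart from the stated 4/6 boundary, the individual decisions rest on the assumed mTPI settings. The expected frequency is low and cannot be quantified. It is worth correcting because the event concerned is the primary endpoint.

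**What to change.** In Section 5.1.4, add to the three bullets the condition that the participant has not had a DLT, as the chemotherapy bullet already does. State that any participant with a DLT in the 21- or 28-day window is evaluable, counted at the assigned dose level and not replaced, whatever follows. Cross-refer to Section 10.5.1 so that dose decisions and the reported DLT rate use the same evaluable set. The cost is one phrase in three bullets, one sentence and one cross-reference, with no extra data or participants.
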